##### **Hyp 1.2. Alternative hypothesis, adults in the EXP group will show a direct effect of better social communication with novel peers (CASS).**

It is plausible that participation in the theatre program more broadly increases salience of social stimuli, leading to enhanced performance on face memory and social communication, which ultimately impact functional outcomes. In this way, successfully interacting and performing with supportive expert social models (peers) increases intrinsic social interest directly contributing to enhanced interactive communication and behavior . Thus, we will test this expanded salience model by including social communication (CASS aggregated score) in the aforementioned model.

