##### **Aim 1: To Assess Preliminary Effectiveness via Target Engagement of Social Salience.**

Hyp 1.1. Adults with ASD in the EXP group will demonstrate significantly faster growth in IMF (primary DV), CMF (secondary DV) or WMS-F (secondary DV) than adults with ASD in the WLC group, verifying the intervention had predicted effect on the target.

**Statistical Analysis:** IMF is the primary DV because it uses the same procedure, stimuli, and metric that was used with our previous successful efficacy demonstrations of SENSE Theatre. The CMF and WMS-F are measures of the same constructs on which SENSE Theatre had effects in children and adolescents, but are measured with procedures appropriate for adults. Thus, the latter two variables are considered secondary. The effect on the primary and secondary dependent variables will be tested in separate analyses for posttest and follow-up measures. In each analysis, we will use multiple linear regression in which group (experimental = EXP or waitlist control = WLC) is analyzed as the dummy-coded independent variable, and the baseline (pre-intervention) variable is analyzed as a covariate (assuming homogeneity of slopes assumption is met). By including the baseline value as a covariate, the coefficient for group becomes the between-group (EXP vs. WLC) difference in the pre-test adjusted posttest (or follow-up) scores (i.e., a measure of change similar to residualized gain scores). This method is often superior to a method that uses raw change scores directly because it improves the statistical power of the significance test and improves the accuracy of effect size estimates relative to between-group differences in raw change scores . If significant difference between groups are detected on other baseline variables that correlate with the outcome, those baseline variables will also be controlled in the multiple linear regression model, assuming appropriate assumptions are met. We will assess the homogeneity of slopes assumption by testing the interaction effect between baseline variable and treatment group assignment. If there is a significant interaction, then we will assess the treatment effect at various levels of the pre-intervention variable. If other regression assumptions (e.g., homoscedasticity, normality of residuals) are not met, robust standard error estimates will be used to test parameters in analogous models.

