**Power analyses for tests of hypothesis associated with Aim 1.** Using a one-tailed test (based on the a priori predicted direction of differences), 80% power, 5% type 1 error, and a post-attrition sample size with equal groups of 40 (20 in each group), the minimal detectable effect size is an  $R^2$  of 0.14 (i.e., standardized mean difference of .80). The effect size of the between-group difference on the pretest-adjusted posttest ERP measure of memory for faces in our most recent RCT of SENSE Theatre was an  $R^2$  of .18 (i.e., standardized mean difference of .94). Therefore, it is feasible that we will detect the predicted SENSE Theatre effect on our primary measure of memory for faces with the proposed sample size.

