##### **Aim 2: Test the Link Between the Degree of Target Engagement (Social Salience), Social Interaction, Anxiety/Depression (STAI, ABCL, CDI) and Functional Outcomes of Social Skills (SRS, ABAS).**

Hyp 2.1: Adults in the EXP group will demonstrate significantly more growth on functional outcomes.

Hyp 2.2: There will be a positive association between (a) memory for faces (IMF, CMF or WMS-F) at post-test or follow-up and (b) social skills (CASS involvement and rapport) at posttest or follow-up.

Hyp 2.3: There will be a negative association between (a) memory for faces (IMF, CMF or WMS-F) at post-test or follow-up and social awareness symptoms (SRS-2 awareness T score), or anxiety/depression (STAI, ABCL, CDI) at posttest or follow-up.

**Statistical Analysis:** The aforementioned statistical analyses in Hyp 1.1 will be followed for Hyp 2.1 with the functional outcomes as the dependent variable. The SRS-2 is the instrument from which we will derive our primary DV because it is the same instrument we have used to show the association between our primary measure of memory for faces and social symptoms in our past work on children and adolescents with ASD. From the SRS-2, the Awareness subscale and its T score will be the subscale and score type used to test this aim because this is the variable that correlates with the primary measure of memory for faces (i.e., the ERP measure). The other measures are secondary DVs because, while they measure similar or identical constructs as those for which SENSE Theatre has had effects in children and adolescents, but these are measured with procedures appropriate for adults in the present proposal. In two separate analysis (one for posttest and one for follow-up), we will examine the association of memory for faces with the primary functional outcome measure using linear regression. We will also explore how changes in social awareness symptoms are related to changes in memory for faces by modeling the social awareness outcomes for all timepoints as a function of the change in memory for faces and a timepoint dummy variable using a generalized estimating equation. To assess the effect of change in memory for faces on change in social awareness symptoms we will test the change in memory for faces by timepoint interaction. Similar analyses will be conducted for secondary DVs.

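### As written, the Hyp 1.2 analysis does not test the treatment effect on CASS, because it adds CASS to a regression whose outcome is face memory

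*SAP*

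**What the plan says.** The Hyp 1.2 heading in SAP section 4.4 makes CASS the thing that treatment changes: "adults in the EXP group will show a direct effect of better social communication with novel peers (CASS". The text below it gives a rationale and one sentence of method: "we will test this expanded salience model by including social communication (CASS aggregated score) in the aforementioned model".

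The only model set out before that sentence is the Hyp 1.1 regression. Its outcomes are the face-memory measures: "significantly faster growth in IMF (primary DV), CMF (secondary DV) or WMS-F (secondary DV". On the predictor side, group "is analyzed as the dummy-coded independent variable, and the baseline (pre-intervention) variable is analyzed as a covariate". Posttest and follow-up are analysed separately. The SAP interprets the group term as follows: "the coefficient for group becomes the between-group (EXP vs. WLC) difference in the pre-test adjusted posttest (or follow-up) scores".

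For Hyp 2.1, under Aim 2, the SAP reuses the same regression and names the role of the new variable: "The aforementioned statistical analyses in Hyp 1.1 will be followed for Hyp 2.1 with the functional outcomes as the dependent variable".

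Under Future Directions, the SAP lists a test of a C path, meaning the treatment effect on social behaviour. It does not name CASS there or give a model.

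**The concern.** The hypothesis and its analysis concern different quantities. The hypothesis is a between-group difference in CASS. The analysis, followed word for word, leaves face memory as the outcome and adds CASS to the equation. An analyst could carry it out faithfully and have no estimate of the effect that Hyp 1.2 is about.

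Two things are at stake. First, Hyp 1.2 is one of two hypotheses under Aim 1, and the SAP says the results will inform a Go/No-Go decision. If the role of CASS is open, it can be settled after the data are seen, in a plan that makes no alpha adjustment. Second, one way of filling the gap is to enter posttest CASS as a predictor. That conditions a randomised comparison on something treatment is expected to change, and the resulting group term could be misread as a treatment effect on face memory.

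**Working it through.** **1. What each term of the literal model estimates.** Adding CASS to the Hyp 1.1 regression gives

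face memory = b0 + b1·group + b2·baseline face memory + b3·CASS + error.

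- If CASS is the baseline score, b1 is still a randomised effect on face memory and b3 is a baseline association.
- If CASS is the posttest or follow-up score, b1 is a face-memory difference at equal CASS and b3 is an association between CASS and face memory within arms.

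In neither case does a coefficient estimate the EXP minus WLC difference in CASS. This step needs no numerical assumption.

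**2. The SAP's own power figure.** Inputs from the Aim 1 power paragraph: 20 per arm, one-tailed 5%, 80% power, minimal detectable effect 0.80 (R² 0.14), earlier effect on the ERP measure 0.94 (R² 0.18).

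- Noncentrality at 0.80: 0.80 × √(20/2) = 2.53. With 37 degrees of freedom, power is 79.9%, so the stated figure reproduces.
- R² = d²/(d² + 4): 0.64/4.64 = 0.138 and 0.8836/4.8836 = 0.181, as stated.
- Power at 0.94: 0.94 × √10 = 2.97, which gives 89.8%, about 90%.

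**3. If posttest CASS were a covariate.** The documents give neither a CASS effect (d_CASS) nor a within-arm IMF–CASS correlation (r), so both are assumptions. Scores are scaled to a within-arm SD of 1 after baseline adjustment.

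- Group coefficient: d_IMF − r·d_CASS
- Residual SD: √(1 − r²)
- Variance inflation, because group and CASS are correlated: 1 + d_CASS²/4
- Noncentrality: (d_IMF − r·d_CASS) × √10 / √[(1 − r²)(1 + d_CASS²/4)], with 40 − 4 = 36 degrees of freedom

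Example with d_CASS = 0.8 and r = 0.5: coefficient 0.94 − 0.40 = 0.54; noncentrality 0.54 × 3.162 / √(0.75 × 1.16) = 1.83; power 56%.

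| d_CASS | r | Coefficient | Power, formula | Power, simulation |
|---|---|---|---|---|
| 0.5 | 0.3 | 0.79 | 80% | 78% |
| 0.5 | 0.5 | 0.69 | 77% | 75% |
| 0.8 | 0.3 | 0.70 | 68% | 66% |
| 0.8 | 0.5 | 0.54 | 56% | 54% |
| 0 | 0.3 to 0.5 | 0.94 | 92% to 96% | 91% to 95% |
| 0.5 to 0.8 | 0 | 0.94 | 88% to 86% | 86% to 83% |

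The simulation used 20,000 trials per row setting, 20 per arm, and ordinary least squares with a baseline covariate. The formula runs slightly high because it treats the variance inflation as fixed.

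If the true IMF effect were zero and d_CASS were 0.8, the expected coefficient would be −0.3 × 0.8 = −0.24 to −0.5 × 0.8 = −0.40. If r and d_CASS had opposite signs, the coefficient would rise: r = −0.2 with d_CASS = 0.8 gives 0.94 + 0.16 = 1.10. Hyp 1.2 and Hyp 2.2 together predict the same sign, and hence attenuation, provided the association in Hyp 2.2 also holds within arms.

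**4. With CASS as its own outcome.** The model has the form checked in step 2, so with 20 per arm the minimal detectable CASS effect is again 0.80.

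**The case against.** The strongest reply is that the text calls CASS neither a covariate nor a posttest measure. Where the SAP means a covariate it generally says so, and here it says only that CASS is included. The heading makes CASS the effect, and the rationale treats face memory and social communication as parallel consequences of the programme. On that view the sentence is shorthand for running CASS through the same regression as another outcome. Even a covariate reading could mean baseline CASS, since the extra covariates that Hyp 1.1 allows are baseline variables; that would bias nothing.

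Most of this stands. A reader might infer that the SAP commits to adjusting for posttest CASS, and the documents do not support that: role and time point are both open. What the reply does not supply is the missing test. The outcome reading needs words that Hyp 2.1 contains and Hyp 1.2 does not, and baseline CASS as a covariate still gives no estimate of a CASS effect.

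A reader might also infer that the primary IMF analysis is diluted. It is not. Hyp 1.1 is specified in full without CASS, its power statement refers to that test, and nothing in Hyp 1.2 replaces it.

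Finally, a reader might infer that the SAP nowhere intends to test treatment on social behaviour. The C path shows that it does, but without naming CASS or giving a model. Nor does Hyp 2.1 clearly fill the gap: the Aim 2 heading identifies its functional outcomes as SRS and ABAS and lists social interaction separately.

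**Conclusion.** The point holds as a mismatch between hypothesis and analysis: read literally, the Hyp 1.2 model contains no estimate of the treatment effect on CASS. This follows from the text alone.

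The attenuation is conditional. It applies only if posttest or follow-up CASS is entered as a predictor, and only to that additional model. Its size, a coefficient of 0.79 down to 0.54 and power of about 79% down to 55%, rests on an assumed CASS effect of 0.5 to 0.8 SD and an assumed r of 0.3 to 0.5. A spurious negative coefficient would require posttest CASS as a covariate together with no true IMF effect, a real CASS effect and a positive r.

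This should be corrected before analysis, because Hyp 1.2 feeds the Go/No-Go decision. It does not threaten the primary analysis, and the hypothesis is labelled an alternative one in a pilot trial.

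**What to change.** Replace the analysis sentence under Hyp 1.2 with: *Hyp 1.2 will be tested with the Hyp 1.1 regression, with the CASS aggregated score at posttest (and, separately, at follow-up) as the dependent variable, group as the independent variable and baseline CASS as the covariate.*

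Add that any model entering posttest or follow-up CASS as a predictor of face memory is exploratory and will not be used to test a treatment effect. In the same edit, define the aggregated score, since Hyp 2.2 refers to CASS involvement and rapport instead.

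The cost is a few lines of SAP text. The protocol already schedules the CASS at the pre, post and follow-up visits, so no new data are needed.

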##### **Aim 2: Test the Link Between the Degree of Target Engagement (Social Salience), Social Interaction, Anxiety/Depression (STAI, ABCL, CDI) and Functional Outcomes of Social Skills (SRS, ABAS).**

Hyp 2.1: Adults in the EXP group will demonstrate significantly more growth on functional outcomes.

Hyp 2.2: There will be a positive association between (a) memory for faces (IMF, CMF or WMS-F) at post-test or follow-up and (b) social skills (CASS involvement and rapport) at posttest or follow-up.

Hyp 2.3: There will be a negative association between (a) memory for faces (IMF, CMF or WMS-F) at post-test or follow-up and social awareness symptoms (SRS-2 awareness T score), or anxiety/depression (STAI, ABCL, CDI) at posttest or follow-up.

**Statistical Analysis:** The aforementioned statistical analyses in Hyp 1.1 will be followed for Hyp 2.1 with the functional outcomes as the dependent variable. The SRS-2 is the instrument from which we will derive our primary DV because it is the same instrument we have used to show the association between our primary measure of memory for faces and social symptoms in our past work on children and adolescents with ASD. From the SRS-2, the Awareness subscale and its T score will be the subscale and score type used to test this aim because this is the variable that correlates with the primary measure of memory for faces (i.e., the ERP measure). The other measures are secondary DVs because, while they measure similar or identical constructs as those for which SENSE Theatre has had effects in children and adolescents, but these are measured with procedures appropriate for adults in the present proposal. In two separate analysis (one for posttest and one for follow-up), we will examine the association of memory for faces with the primary functional outcome measure using linear regression. We will also explore how changes in social awareness symptoms are related to changes in memory for faces by modeling the social awareness outcomes for all timepoints as a function of the change in memory for faces and a timepoint dummy variable using a generalized estimating equation. To assess the effect of change in memory for faces on change in social awareness symptoms we will test the change in memory for faces by timepoint interaction. Similar analyses will be conducted for secondary DVs.

**Power analyses for tests of primary dependent variable in Aim 2:** A one-tailed test of the association between memory for faces and social awareness symptoms is reasonable because past evidence indicates that association is negative and the theory predicting the association indicates that the association should be negative. Using a one-tailed test, 80% power, and 40 post-attrition sample size, the minimally-detectable effect size for the association between memory for faces and social awareness symptoms is an R square value of 0.16. In our past work, the association between ERP-measured memory for faces and SRS-measured social awareness symptom severity was  $R^2 = 0.15$ . Thus, it is feasible that we will detect the expected association between memory for faces and social awareness symptom severity with a post-attrition sample size of 40.

**Interpretative framework for findings detected in the context of multiple significance testing without alpha adjustment.** The R33 funding mechanism is designed to enable the acquisition of preliminary data to aid the design of more robust tests of the efficacy of treatments. Adjusting alpha for multiple significance testing at this early stage would increase the probability of Type II error. Therefore, the results will be considered pilot given the inflation of type 1 error resulting from using multiple significance tests to address the same aim. The pilot findings will provide the preliminary data needed to plan for a future, larger RCT.

**The aforementioned design is rigorous and the results from the analyses will set the stage to inform Go/No-Go decisions as to whether further development or testing of the intervention in a larger sample of adult participants with ASD is warranted.**

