#### 4.4. Statistical Design and Power

**Post-attrition Sample Size Used to Test Aims and Compute Statistical Power.** We propose to recruit approximately 46 participants to enroll 40 participants over the first 2 years of the project with the last year being used to complete the treatment and assessment for the last wave of recruitment. Using a 10% attrition rate, which is the maximum attrition rate to date of past SENSE Theatre trials, the post-attrition sample size will be 40 (equally distributed between experimental and control groups). The analyses and power analyses are based on post-attrition sample size and past findings involving the primary dependent variables.

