#### **Future Directions:**

Ultimately, we hope to test the hypothesis that SENSE Theatre will have a proximal effect on social cognition that will act as a mediator on social behavior/functioning. Creating composites should enhance power by increasing the reliability and thus validity of construct estimates and reduce the number of significance tests. If confirmed, then such suggests that the theory and data must be mature enough for us to expect replication and thus a probable contribution to cumulative knowledge building.

For the R33, the sample size will not allow us to test a mediation model. Instead we will test the A path (SENSE Theatre effect on social cognition) and B path (the association between Social Cognition and Social Behavior controlling for treatment effects on Social Behavior) and the C path (SENSE Theatre effect on Social Behavior). These data can help create the foundation for an R01 with adults by: A) indicating whether the association among the component variables really is  $> .4$  for each construct and if not indicating which component variables are associated as expected with other constructs. B) If the target is engaged and linked to functional outcomes that have clinical significance for adults with ASD, then the data will serve as a base for future R01 sample size to

power tests of the mediated model.

As in our current R01, a larger RCT will allow us to use a multivariate multilevel growth model (involving a linear growth model for memory and another linear growth model for social behavior). We would be able to specify a mediation pathway at the participant-level from treatment (x) through memory for faces (m) to social behavior (y). The indirect effect could then be tested using the 95% confidence interval around the product of the unstandardized coefficients for the  $(x \rightarrow m)$  and  $(m \rightarrow y)$  paths of the multilevel mediation model following procedures of Lachowicz, Sterba, and Preacher. The confidence interval will be estimated using the Monte-Carlo procedure described in Preacher and Selig,.

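### The Aim 2 minimum detectable R² of 0.16 does not follow from its inputs (0.138 to 0.150) and exceeds the R² of 0.15 called feasible to detect

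*SAP*

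**What the plan says.** The SAP, section 4.4, Aim 2, plans a test in which "we will examine the association of memory for faces with the primary functional outcome measure using linear regression", once at posttest and once at follow-up. That sentence names no covariate. The power paragraph for the Aim 2 primary dependent variable sets its inputs as "Using a one-tailed test, 80% power, and 40 post-attrition sample size" and reports that "the minimally-detectable effect size for the association between memory for faces and social awareness symptoms is an R square value of 0.16". It then gives the association found in past work as R² = 0.15 and concludes: "Thus, it is feasible that we will detect the expected association between memory for faces and social awareness symptom severity" with 40 participants after attrition.

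Three other places in the SAP bear on the calculation:

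- The Aim 1 power paragraph is the only one that states an alpha: "80% power, 5% type 1 error", one-tailed, 20 per group. Its minimum is R² = 0.14 ("i.e., standardized mean difference of .80"), set against a past R² of .18.
- The opening paragraph of section 4.4 says that "the post-attrition sample size will be 40 (equally distributed between experimental and control groups"), so 40 is already net of attrition.
- Future Directions describes the B path as "the association between Social Cognition and Social Behavior controlling for treatment effects on Social Behavior", which suggests that treatment group might be a covariate in some version of this model.

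**The concern.** There are two separate problems. The first needs no calculation: the past effect (0.15) is smaller than the minimum the plan says it can detect at 80% power (0.16), yet the text draws feasibility from that comparison. The matching Aim 1 argument has the two numbers in the right order (.18 against 0.14). The second is that 0.16 does not come out as an R² from the inputs given.

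This is the only power statement for the primary dependent variable of Aim 2, and the SAP says its results will inform the decision on whether to go further with the intervention. A reader who takes 0.16 at face value will infer that the trial has less than 80% power for the effect it expects.

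**Working it through.** **Inputs.** One-tailed test, 80% power and N = 40 come from the Aim 2 power paragraph. Alpha = 5% is carried over from the Aim 1 power paragraph and is an assumption. One predictor (k = 1) is used because the Aim 2 analysis names no covariate.

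**Aim 1 figure first.** Noncentral t, 20 per group, df = 38, one-sided 5%: the minimum standardized difference for 80% power is d = 0.801. With equal groups R² = d²/(d² + 4) = 0.641/4.641 = 0.138. This reproduces the SAP's .80 and 0.14, so the 5% alpha and the regression t method fit how the SAP authors worked.

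**Aim 2 minimum R² by three standard methods.**

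1. *Regression t test, fixed predictor.* Noncentrality = √(N·f²), df = N − k − 1 = 38, critical t = 1.686. Power of 80% needs a noncentrality of 2.532, so f² = 2.532²/40 = 0.1603 and R² = f²/(1 + f²) = 0.1603/1.1603 = **0.138**.
2. *Exact bivariate normal, random predictor.* The same noncentral t, averaged over a chi-square with N − k = 39 df in place of N, gives R² = **0.146**.
3. *Fisher z.* r = tanh[(1.645 + 0.842)/√37] = tanh(0.4088) = 0.3874, so R² = **0.150**.

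**Power at the two R² values in the text (N = 40, k = 1).**

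| Method | Minimum R² | Power at 0.15 | Power at 0.16 |
|---|---|---|---|
| Regression t | 0.138 | 83.3% | 85.7% |
| Exact, random predictor | 0.146 | 81.0% | 83.4% |
| Fisher z | 0.150 | 80.0% | 82.4% |

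If 0.16 were the 80% minimum, power at 0.16 would be 80%. It is 82% to 86%.

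**Inputs that might give 0.16.**

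- *Two-sided 5%, N = 40:* 0.171, 0.181, 0.185. Sidedness does not explain it.
- *f² printed as R²:* f² = 0.160 by method 1, and 0.16/1.16 = 0.138. The number matches, but the documents do not confirm it.
- *One covariate (k = 2):* 0.138, 0.150, 0.154, with power at 0.15 of 83.2%, 80.1%, 79.0%.
- *Two covariates:* 0.158 by Fisher z, which rounds to 0.16; power at 0.15 is then 78.0%. The exact method gives 0.153 (79.1%).
- *Three covariates:* 0.157 (exact) and 0.162 (Fisher z).
- *N = 36, one-tailed:* 0.152, 0.161, 0.166. *N = 46, two-sided:* 0.151, 0.159, 0.162. Both contradict the stated N of 40, and the second also contradicts the stated one-tailed test.
- *A smaller one-sided alpha at N = 40:* 0.032 to 0.041, depending on method. Power at 0.15 would then be about 77%.

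**How thin the margin is.** As a sensitivity check only, since 40 is already post-attrition, power at 0.15 with N = 36 would be 79.5%, 77.1% or 75.9%. As N falls, the minimum first exceeds 0.15 at N = 36 (regression t, 0.152) or N = 38 (exact, 0.153). Under Fisher z it already equals 0.15 at N = 40.

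**The case against.** The strongest reply is that 0.16 may be right and merely under-documented. Alpha is not stated in this paragraph, and the regression may have been meant to carry covariates: the Aim 1 model adjusts for baseline, and the B path in Future Directions controls for treatment. Two covariates under Fisher z, or three under either Fisher z or the exact method, round to 0.16. The f² explanation is then one candidate among several. A correlation of about 0.39 rounded up to .4 before squaring would also give 0.16. It can further be said that feasible is not a promise of 80% power, that a gap of 0.01 in R² is small, and that the SAP calls its findings pilot.

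Part of this stands. The source of 0.16 cannot be settled from the documents, and the correction must leave room for undisclosed inputs. It does not rescue the paragraph. Each of those covariate or alpha routes needs an input that the SAP does not state, and if 0.16 is the true minimum the past effect still falls below it. The gap is small, but 0.15 lies between the printed value and the regression and exact results, so the error reverses the one comparison the paragraph is there to make.

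**Conclusion.** The concern holds. On the stated inputs, with 5% one-sided alpha taken from Aim 1 and no covariate, the minimum detectable R² is 0.138 to 0.150 and not 0.16. As printed, the paragraph also contradicts itself, whatever alpha or method was used. The error understates sensitivity: power at R² = 0.15 is 80.0% to 83.3%, so the feasibility conclusion is supportable, with almost no margin under Fisher z. With one covariate, power is 79% to 83%, and with two it can fall to 78%. This is a reporting error that should be corrected; it does not invalidate the design.

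**What to change.** Revise the Aim 2 power paragraph to state alpha, the calculation method and the covariates, and correct the figure to match. If the intended inputs are those assumed here, suitable text is: *With a one-tailed test at 5% type 1 error, 80% power, a single predictor without covariates and 40 post-attrition participants, the minimum detectable R² is 0.14 by the regression t test, or about 0.15 if memory for faces is treated as random. Power at the previously observed R² of 0.15 is about 80% to 83%.* The feasibility sentence can then stay, with the thin margin acknowledged. The value f² = 0.16 should be added only if the sponsor confirms that it was the source.

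If treatment group or another covariate is intended, name it in the Aim 2 analysis and restate the figures (one covariate: minimum 0.138 to 0.154, power at 0.15 of 79% to 83%). If 0.16 came from other inputs, state them and reword the feasibility sentence, because the expected effect would then be below the minimum.

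The cost is one SAP paragraph, plus a covariate statement in the Aim 2 analysis if one is intended. Sample size, hypotheses and conduct are unaffected.
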